--	--

	
 
- For patients receiving 75 mg Q2W:           
 
o If LDL-C <25 mg/dL (0.65 mmol/L) but ≥ 15 mg/dL (0.39 mmol/L) on 2 consecutive measurements: alirocumab will be continued but additional monitoring will be implemented, to further confirm the safety of low LDL-C levels.
 
o If LDL-C <15 mg/dL (0.39 mmol/L) on 2 consecutive measurements: alirocumab treatment will be discontinued at the next visit. In order to maintain the blind there will be blinded substitution to placebo injections for the remaining duration of the study. Additional monitoring will be implemented until the study treatment discontinuation is done.
 
 
 
 
As lipid values will not be communicated to investigators after randomization to maintain the blind, the continuation of the 75 mg dose, the up-titration to the 150 mg dose, the down-titration from 150 to 75 mg, or discontinuation will occur automatically, without site or patient awareness. Moreover, blinded dose adjustment will avoid the need for dummy titrations in the placebo group.
 
Atorvastatin or rosuvastatin daily dose, as well as dose of other non-statin LMT (if applicable), is required to be stable from randomization up to the end of the study, unless safety reasons prompt dose reduction or discontinuation.
 
Patients should be on stable diet (NCEP-ATPIII TLC diet or equivalent) throughout the entire study duration from screening to the end of the study.

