#### 10.4.4 General guidelines for reporting adverse events

- AEs are to be recorded in corresponding screen(s) included in the eCRF.
- The reporting requirement of AEs depends on patient status (study completer or patient who had premature permanent discontinuation of IMP)
  - In patients who receive IMP until the end of the study (study completer), all AEs, regardless of seriousness or relationship to IMP/NIMP, spanning from the signature of the informed consent form until the CSED visit are to be recorded in the eCRF. Patients who experience a new or ongoing related or serious AE or a new or ongoing AESI (see [Section 10.4.2](#)) at the CSED visit should be followed beyond the CSED visit until resolution, stabilization, or death (whichever comes first) and related data will be collected (see [Section 10.1.5.4.1](#)).
  - In patients who have permanent premature IMP discontinuation:
    - All AEs, regardless of seriousness or relationship to IMP/NIMP, spanning from the signature of the informed consent form until 6 months following V70 (end of treatment visit) are to be recorded in the eCRF.
    - From 6 months following V70 until the CSED visit, related and/or serious AEs should be recorded in the eCRF.

***NOTE:** Reporting requirement for suspected efficacy endpoints is the same regardless of patient status (study completers or patients who had premature permanent discontinuation of IMP); suspected efficacy endpoints should be reported in all randomized patients until the end of the study (CSED).*

- Whenever possible, diagnosis or single syndrome should be reported instead of symptoms. The Investigator should specify the date of onset, intensity, action taken with respect to IMP, corrective treatment/therapy given, additional investigations performed, outcome, and his/her opinion as to whether there is a reasonable possibility that the AE was caused by the IMP.
- When treatment is prematurely discontinued, the patient will be maintained in the study and the patient's observations will continue until the common study end date visit (see [Section 10.3.4](#)).
- Laboratory, vital signs or ECG abnormalities are to be recorded as AEs only if:
  - Symptomatic and/or
  - Requiring either corrective treatment or consultation, and/or
  - Leading to IMP discontinuation or modification of dosing (with exception of LDL-C levels which may lead to IMP dosing modification, but in a blinded manner), and/or

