3.1.4 Safety endpoints

Following injections are considered as double-blind IMP injections:

• For patients randomized in the placebo group: any injection from double-blind kits;

• For patients randomized in the alirocumab group: any injection from double-blind kits excepted placebo injections given to maintain the blind in case of 2 consecutive LDL-C values <15 mg/dL.

Of note potential additional training injections after randomization using training injection kits will not be taken into account.

The period of safety observation starts from the time when the patient gives informed consent and is divided into three periods:

- PRE-TREATMENT period: defined from the signed informed consent up to the first dose of double-blind IMP injection;
- Treatment-emergent adverse event (TEAE) period: defined as the time from the first dose of double-blind IMP injection to the last dose of double-blind IMP injection +70 days (10 weeks), (as residual effect of treatment is expected until 10 weeks after the stop of double-blind IMP).

The TEAE period will include:

- The TREATMENT period defined as the time from the first dose of double-blind IMP up to the day of last dose of double-blind IMP injection +21 days, as serum concentration of alirocumab >10 μ g/mL is expected for approximately 21 days following administration of 150 mg, and because throughout the previous studies it was observed that when alirocumab concentrations declined below this concentration, decrease in effect on LDL-C is observed.
- The RESIDUAL TREATMENT defined as the time from the day of last dose of double-blind IMP injection +22 days up to the day of last dose of double-blind IMP injection +70 days (10 weeks).
- POST-TREATMENT period: defined as the time starting the day after the end of the TEAE period.

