3.4.5 Analyses of safety data

The summary of safety results will be presented by treatment group.

General common rules

All safety analyses will be performed on the safety population as defined in Section 3.3.2, unless otherwise specified, using the following common rules:

- Safety data in patients who do not belong to the safety population (ie, exposed but not randomized) will be listed separately;
- The baseline value is defined as the last available value before first double-blind IMP injection, except otherwise specified;
- The potentially clinically significant abnormality (PCSA) values are defined as abnormal values considered medically important by the Sponsor according to predefined criteria/thresholds based on literature review and defined by the Sponsor for clinical laboratory tests, vital signs, and ECG (see Appendix A). In case the PCSA threshold is within the normal laboratory ranges, the analysis will be done using "<LLN" or ">ULN" threshold instead of "<PCSA threshold" or ">PCSA threshold" respectively. Of note, for HbA_{1c}, usual PCSA criteria will not be applied as specific analysis for the incidence of diabetes during the TEAE period will be provided, combining information from adverse event, laboratory parameters, and antidiabetic medications (see detail in Section 3.4.5.3).
- PCSA criteria will determine which patients had at least 1 PCSA during the TEAE period, taking into account all evaluations performed during this period, including nonscheduled, local or repeated evaluations.
- The treatment-emergent PCSA denominator by group for a given parameter will be based on the number of patients assessed for that given parameter in the TEAE period by treatment group on the safety population.
- All measurements, scheduled or unscheduled, fasting or not fasting, will be assigned to analysis windows defined in Section 3.5.4 Table 8.
- For quantitative safety parameters based on central laboratory/reading measurements, descriptive statistics will be used to summarize results and change from baseline values by visit (using analysis windows defined in Section 3.5.4 Table 8) and treatment group. Summaries will include the last on-treatment value and the worst on-treatment value.
- The worst value is defined as the nadir and/or the peak value during the treatment period according to the direction (minimum or maximum) of the abnormality as defined in the PCSA list.

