3.4.5.1 Analyses of adverse events

Generalities

The primary focus of adverse event reporting will be on TEAEs. Pre- and post-treatment adverse events will be described separately.

If an adverse event date/time of onset (occurrence, worsening, or becoming serious) is incomplete, an imputation algorithm will be used to classify the adverse event as pre-treatment, treatment-emergent, or post-treatment. The algorithm for imputing date/time of onset will be conservative and will classify an adverse event as treatment emergent unless there is definitive information to determine it is pre-treatment or post-treatment. Details on classification of adverse events with missing or partial onset dates are provided in Section 3.5.3.

Adverse event incidence tables will present by SOC, HLGT, HLT, and PT, sorted in alphabetical order for each treatment group, the number (n) and percentage (%) of patients experiencing an adverse event. Multiple occurrences of the same event in the same patient will be counted only once in the tables within a treatment phase. The denominator for computation of percentages is the safety population within each treatment group.

Sorting within tables should ensure the same presentation for the set of all adverse events within the observation period (pre-treatment, treatment-emergent, and post-treatment). For that purpose, the table of all TEAEs presented by SOC and PT sorted by the internationally agreed SOC order and decreasing frequency of PTs within SOCs will define the presentation order for all other tables unless otherwise specified. Sorting will be based on results for the alirocumab group.

As recommended by the safety planning, evaluation, and reporting team (SPERT, [6]) the analysis of all TEAEs will be split into 3 tiers for signal detection and analysis of adverse events.

- Tier 1: TEAEs with pre-specified detailed analysis: TEAEs for which hypothesis and comprehensive analytical approach are prospectively defined.
- Tier 2: signal detection among common TEAE: (not prespecified).
- Tier 3: descriptive analysis of infrequent TEAEs: TEAEs which are infrequent. This could include some AESI predefined in the protocol (eg, pregnancy, hemolytic anemia) to ensure close monitoring but which are expected to be so rare that statistical analysis is not meaningful. For those events, medical judgment should prevail.

Prospective analysis for Tier 1 events

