- All treatment-emergent SAEs by primary SOC, HLGT, HLT, and PT, sorted by the internationally agreed SOC order. The other levels (HLGT, HLT, PT) will be presented in alphabetical order;
- All treatment-emergent SAEs regardless of relationship and related to IMP, by primary SOC, HLGT, HLT, and PT, sorted by the internationally agreed SOC order. The other levels (HLGT, HLT, PT) will be presented in alphabetical order;
- All treatment-emergent SAEs by primary SOC and PT.

Analysis of all treatment-emergent adverse event(s) leading to permanent treatment discontinuation

- All treatment-emergent adverse events leading to treatment discontinuation, by primary SOC, HLGT, HLT, and PT, sorted by the internationally agreed SOC order. The other levels (HLGT, HLT, PT) will be presented in alphabetical order;
- All TEAEs leading to treatment discontinuation by primary SOC and PT.

Analysis of pre-treatment and post-treatment adverse events

- All pre-treatment adverse events by primary SOC and PT sorted by the internationally agreed SOC order and decreasing incidence of PTs within each SOC;
- All pre-treatment adverse events leading to treatment discontinuation (if any) by primary SOC and PT, sorted by the internationally agreed SOC order and decreasing incidence of PTs within each SOC;
- All post-treatment adverse events by primary SOC and PT, sorted by the internationally agreed SOC order and decreasing incidence of PTs within each SOC;
- All post-treatment SAEs by primary SOC and PT, sorted by the internationally agreed SOC order and decreasing incidence of PTs within each SOC.

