3.5 DATA HANDLING CONVENTIONS

3.5.1 General conventions

The following definitions/formulas will be used for computation of parameters.

Common study end date

The common study end date is defined as the date when 1613 patients have experienced at least 1 primary efficacy event or 24 months after the last date of randomization ex-China, whichever comes last.

Date of last dose of investigational medicinal product

The date of the last dose of IMP is equal to the last date of administration reported on the IMP administration case report form page, or missing if the last administration date is unknown. For patients on the alirocumab arm who will switch to placebo injection due to blinded treatment discontinuation, the date of last administration reported associated to an active injection will be considered.

Renal function formulas

eGFR value will be derived using the Modification of the Diet in Renal Disease (MDRD) equation:

175 x (creatinine in μ mol/L / 88.4)^{-1.154} x (age in years)^{-0.203} (x 0.742 if female, x 1.212 if race is "black or african american").

Lipids variables, laboratory safety variables, hs-CRP

For data below the lower limit of quantification (LLOQ)/limit of linearity, half of the lower limit value (ie, LLOQ/2) will be used for quantitative analyses. For data above the upper limit of quantification (ULOQ) / limit of linearity, the upper limit value (ie, ULOQ) will be used for quantitative analyses.

The above rules won't be applied for the calculated LDL-C and non-HDL-C when HDL-C value is below the LLOQ. The value of LLOQ/2 for HDL-C will be used to obtain the non-HDL-C and calculated LDL-C used for quantitative analyses.

Below is an example of data for a dummy patient reported in the database, with the values that will be used in quantitative analyses for each parameters.

Parameter	Value reported in the database	Value used in the analysis	
 TC	255 mg/dL	255 mg/dL	_
HDL-C	<10 mg/dL	5 mg/dL	
Calculated LDL-C ^a	<221 mg/dL	216 mg/dL	
NON-HDL-C	<255 mg/dL	250 mg/dL	
TRIG	172 mg/dL	172 mg/dL	

Table 7 - Example of lipid data for a dummy patient

a Friedewald formula for calculated LDL-C (when lipid expressed in mg/dL: LDL-C=NON-HDL-C-0.2*TG)

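### The by-arm post-treatment adverse event tables are not like-for-like: alirocumab patients switched blindly to placebo add a group with wider and longer recording that the placebo arm cannot have

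*SAP*

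**What the plan says.** **The table.** SAP 3.4.5.1 lists "All post-treatment adverse events by primary SOC and PT", followed by post-treatment serious events. SAP 3.4.5.2 adds post-treatment events leading to death. The general rules are "The summary of safety results will be presented by treatment group" and "The denominator for computation of percentages is the safety population within each treatment group". For these tables the SAP plans no split by how treatment ended and no person-time rate.

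**When the period starts.** SAP 3.1.4: "POST-TREATMENT period: defined as the time starting the day after the end of the TEAE period". The treatment-emergent period ends 70 days after the last double-blind injection.

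**Blinded switch.** After two consecutive LDL-C values below 15 mg/dL on 75 mg, the Protocol summary says: "In order to maintain the blind there will be blinded substitution to placebo injections for the remaining duration of the study". Protocol 6.1.4 adds that neither site nor patient knows of it, and that the placebo group needs no dummy titration. In the alirocumab group, SAP 3.1.4 counts as double-blind product "any injection from double-blind kits excepted placebo injections given to maintain the blind in case of 2 consecutive LDL-C values <15 mg/dL". SAP 3.5.1 dates the last dose of a switched patient accordingly: "the date of last administration reported associated to an active injection will be considered".

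**Recording of events.** Under Protocol 10.4.4, patients on injections to the end of the study have all events recorded to the common study end date (CSED) visit. After open permanent discontinuation, all events are recorded until 6 months after V70, and then: "From 6 months following V70 until the CSED visit, related and/or serious AEs should be recorded in the eCRF". Protocol 10.3.4 and the flow chart notes in 1.2.1 agree. Protocol 10.1.1 and SAP 3.1.4.1, however, state collection to study end without mentioning the narrowing.

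**The concern.** Three kinds of patient could feed the table.

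- **Completers** contribute almost nothing. Protocol 10.1.5.4 sets the final visit 14 days (±3) after the last injection, inside the 70-day window.
- **Open discontinuers**, in both arms, contribute a few months of full recording and then a narrower scope.
- **Blinded-switched patients**, on alirocumab only, are post-treatment for the SAP but on treatment for the site. No V70 is triggered, and every event is recorded until the CSED visit unless the patient later stops injections openly.

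The third group adds both a wider scope and extra post-treatment time to one column. An excess of late, mostly minor events could then appear on alirocumab with no drug effect at all. It would come from the patients with the lowest LDL-C, where Protocol Section 4 says safety information is limited, so it could be misread as a late signal of low LDL-C. The extra one-arm time also reaches the post-treatment serious and fatal event tables, although serious events are collected from everyone to the end.

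**Working it through.** The documents state no post-treatment event figure to reproduce and no expected number of switches. The size is therefore an illustration on assumptions.

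**Step 1. Full recording inside the post-treatment period (70 days = 2.3 months).**

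- Open discontinuer, V70 0 to 1 month after the last dose: 6 − 2.3 = 3.7 months, to 7 − 2.3 = 4.7 months.
- Open discontinuer, V70 3 months after the last dose: 9 − 2.3 = 6.7 months.
- Switched at the earliest point (Month 4) and still injecting: 24 − 4 − 2.3 = 17.7 months with 24 months of follow-up; 64 − 4 − 2.3 = 57.7 months with 64 months.

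**Step 2. Percentages with no drug effect.** Let d be the share openly discontinued (same in both arms), s the share of alirocumab patients switched, and pD and pS the probabilities of at least one recorded post-treatment event in each group:

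- placebo = d × pD
- alirocumab = (1 − s) × d × pD + s × pS

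Assumptions: d = 10% or 20%; s = 1, 3, 5 or 8%; exponential time to first event; any-event rate 0.3 with related/serious rate 0.10 per patient-year, or 0.8 with 0.15; mean post-treatment time 18 months (discontinued) and 24 months (switched); 4.2 months of full recording after open discontinuation.

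Worked case, d = 10%, s = 3%, lower rates:

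- pD = 1 − exp[−(0.3 × 4.2 + 0.10 × 13.8)/12] = 1 − exp(−0.22) = 0.197
- pS = 1 − exp(−0.3 × 24/12) = 0.451
- placebo = 1.97%; alirocumab = 0.97 × 1.97% + 0.03 × 45.1% = 3.27%
- excess 1.29 points (from unrounded values), ratio 1.66

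| Switched (s) | Excess, percentage points | Ratio |
|---|---|---|
| 1% | 0.4-0.8 | 1.10-1.22 |
| 3% | 1.2-2.3 | 1.30-1.66 |
| 5% | 2.1-3.8 | 1.50-2.09 |
| 8% | 3.3-6.1 | 1.80-2.75 |

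**Step 3. Source of the excess.** Give switched patients the same narrowed recording as open discontinuers. In the worked case pS becomes 1 − exp[−(0.3 × 4.2 + 0.10 × 19.8)/12] = 1 − exp(−0.27) = 0.237, and the excess falls from 1.29 to 0.65 points. Across all scenarios about half remains. So about half comes from wider scope and half from post-treatment time without a placebo counterpart.

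**Step 4. Dependence on equal discontinuation.** Take s = 1%, d = 15% on alirocumab, any-event rate 0.5 and related/serious rate 0.125. Then pD = 1 − exp[−(0.5 × 4.2 + 0.125 × 13.8)/12] = 0.273, pS = 1 − exp(−1) = 0.632, and alirocumab = 0.99 × 0.15 × 0.273 + 0.01 × 0.632 = 4.7%. Placebo reaches the same figure at d = 0.047/0.273 = 17.2%. About 2.2 points more open discontinuation on placebo cancels the excess.

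**The case against.** **The group may be tiny.** The switch needs two consecutive values below 15 mg/dL on 75 mg, and Protocol Section 4 expects few patients even below 25 mg/dL. This stands as a limit on size. The same section also reports a substantial proportion below 25 mg/dL in earlier studies, which included higher doses, and the SAP gives switched patients their own disposition reason, exposure summary and date rule. At 1% switched the table still moves by 0.4-0.8 points.

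**The table is descriptive.** SAP 3.4.5.1 puts its primary focus on treatment-emergent events, and no hazard ratio or test is planned for the post-treatment tables. A careful reader could gauge the imbalance from SAP 3.4.3.1, which reports the number switched and patient-years on placebo injections. This stands and limits the consequence, but the table itself would still show two columns that do not compare.

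**Some text says all events are collected to study end.** Protocol 10.1.1 and SAP 3.1.4.1 do, against the specific rules in Protocol 10.3.4 and 10.4.4. Read literally, they remove the scope difference but not the one-arm time. In the worked case with full recording for everyone, pD = 1 − exp(−0.3 × 1.5) = 0.362, placebo is 3.62% and alirocumab 0.97 × 3.62% + 0.03 × 45.1% = 4.87%: an excess of 1.2 points, ratio 1.34.

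**A stronger size might be inferred.** A reader might compare all-event observation time per patient between arms. With 10-20% discontinuation (0.43 years each), 2-8% switched and 1.5-2.5 further years, that ratio runs from (0.20 × 0.43 + 0.02 × 1.5)/(0.20 × 0.43) = 1.4 to (0.10 × 0.43 + 0.08 × 2.5)/(0.10 × 0.43), about 5.6. This is not the inflation of the percentage. A patient counts once per event, so percentages saturate, and related or serious events after V70 + 6 months still enter the table. The 0.43 years is also too narrow an input: the V70 clock starts only when the investigator regards the stop as permanent (Protocol 10.1.5.3), and stops are first treated as temporary (10.3). With V70 six months after the last dose it is (183 + 183 − 70)/365.25 = 0.81 years.

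**Conclusion.** The concern holds. As written, the post-treatment tables compare arms with different recording rules and different observed time, and the difference is built into one arm. The mechanism follows from the text. Its size does not, because the documents give neither a switch rate nor event rates. Under the stated assumptions the artificial excess on alirocumab is about 0.4 to 6.1 percentage points (ratio 1.10 to 2.75), with the low end plausible if few patients switch.

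Two further readings go too far. An excess on alirocumab is not certain: the direction assumes similar open discontinuation in both arms. Nor does the problem reach the main results. Efficacy analyses follow all randomised patients regardless of treatment, and the treatment-emergent analyses stop 70 days after the last active dose.

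**What to change.** In SAP 3.4.5.1, for post-treatment events:

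1. Keep the overall alirocumab column and add two beneath it, blinded-switched and all other patients. The like-for-like comparison with placebo uses the non-switched column. Dropping switched patients altogether is not advised: they have the lowest LDL-C, and the non-switched group is itself defined after randomisation.
2. In open discontinuers, limit the all-event table to V70 + 6 months, and report only serious or related events after that.
3. Use patients with observed post-treatment time as the denominator, and add rates per 100 patient-years, as the SAP already does for treatment-emergent events.
4. Apply the split and the rates to the post-treatment serious event table and to the post-treatment fatal event table in SAP 3.4.5.2.
5. Reconcile Protocol 10.1.1 and SAP 3.1.4.1 with Protocol 10.3.4 and 10.4.4 on how long all events are recorded.

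The cost is SAP wording and a few extra columns in descriptive tables. Switch status and last active injection dates are already derived (SAP 3.4.3.1, 3.5.1 and 3.5.3), so no new data are needed. The change is best made before unblinding.
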